3.1.2. General definitions

Unless specified otherwise in section 3.3 to 3.5, the following definitions will be considered:

- Analysable value will be defined as any non-missing value.
- Baseline value will be defined as the last analysable value prior to the first IMP intake in CL2-95014-002 study (i.e. before or the same date as the first IMP intake date).
- Post-baseline value will be defined as any value recorded at a given timepoint after baseline.
- Change from baseline will be defined as the arithmetic difference between a post-baseline value and the baseline value for a given variable at a given time point.

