1.1.2. Secondary objectives

Secondary objective of this roll-over study is to assess the safety profile of S95014 lyophilizate during the consolidation phase. All adverse events regardless of grade or causality and severity will be collected after the informed consent is signed and during the entire treatment period.

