1.2. Study design

The present CL2-95014-003 study is a multicentre, non-randomized roll-over study of lyophilized Pegaspargase (Oncaspar®, S95014) formulation in the treatment of pediatric patients with ALL who completed the CL2-95014-002 study during the induction phase.

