1.2.1. Study plan

Written informed consent and assent (when appropriate) will be obtained from each patient and/or his/her parent(s)/legal representative during the inclusion visit, corresponding to the withdrawal visit of the initial CL2-95014-002 study.

S95014 lyophilizate will be administered IV every two weeks during the consolidation phase at the dose of 1000, 2000 or 2500 U/m², as per investigator's judgment. Patients will be administered 9 infusions of S95014 lyophilizate, at weeks 7, 9, 11, 15, 17, 19, 23, 25 and 27. Patients will receive other backbone chemotherapy agents as per ALL-MB 2015 protocol (see study protocol Appendix 1).

The study duration will be approximately 7 months, including the treatment period consisting of the consolidation phase and the follow-up period. After completing the consolidation phase, patient will be discontinued from the study and will be treated as per investigator's judgment.

The study will be divided into the following periods for each participant:

- **Inclusion visit:** to obtain informed consent and check the inclusion/non-inclusion criteria. The inclusion visit of CL2-95014-003 study will correspond to the withdrawal visit of the initial CL2-95014-002 study.
- **Treatment period:** As per ALL-MB 2015 protocol, treatment period will start at Day 1 of the consolidation phase. Patients will be on treatment until the end of the consolidation

[figure not shown]

phase, unless they meet a discontinuation criterion as described in the Clinical Study Protocol.

- **Withdrawal visit:** no later than 30 days after the last dose of S95014 during the consolidation phase. Patient will continue receiving backbone chemotherapeutic regimen as per ALL-MB 2015 protocol, according to physician's judgment.
- **Follow-up visit:** should be made after Withdrawal visit, a contact or telephone call will be done not earlier than 30 days after the last S95014 infusion, except in case of consent withdrawal. Follow-up of adverse events and the patient's survival will be recorded.

The study plan is shown in Figure (1.2.1) 1.

Figure (1.2.1) 1 - Study plan

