3.3.3. Demographic data and other baseline characteristics

Demographic and baseline measurements will be summarized for the SAS, using standard descriptive summaries or categorical summaries, as appropriate. In addition to the summary tables, a listing will be provided for all demographic and baseline characteristics data.

In addition, listing of medical history will be provided. For this purpose, data of the CL2-95014-002 study may be used.

The following baseline characteristics will be summarized based on descriptive statistics:

- Age at inclusion (years; if not available, then it will be calculated as the biggest integer $\leq [(ICF\ date - date\ of\ birth + 1) / 365.25]$)
 - As continuous variable
 - By Age Category I (age <10, 10 - <16, and ≥ 16 years)
 - By Age Category II, EudraCT categories (0-27 days, 27 days-23 months, 2-11 years, 12-17 years, 18-65 years, ≥ 66 years)
- Sex
- Race
- Ethnicity
- Height (cm)
- Weight (kg)
- Body Mass Index (BMI (kg/m²) = weight (kg) / height (m²))
- Body Surface Area (BSA(m²) = sqrt (height (cm) x weight (kg) / 3600))

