3.5.2. Other Safety Evaluations

Descriptive statistics of laboratory parameters and continuous variables of vital signs will be calculated for each time point. Shift tables for qualitative urinalysis results at each time point after the first IMP infusion will be created. Height, weight, BSA and BMI will be summarized by visit.

Shift tables will be provided for laboratory parameters to compare a subject's baseline laboratory evaluation relative to the worst value during the treatment period using CTCAE v5.0 grades. In addition, the normal laboratory ranges will be used to evaluate whether a particular laboratory test value was normal, low, or high for each visit value relative to whether or not the baseline value was normal, low, or high. Subjects with abnormal laboratory values will be listed and values outside the normal ranges will be flagged.

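### The laboratory and urinalysis shift tables start from a pre-induction baseline, so they cannot show whether a patient's shift arose in induction or in consolidation; a second set of tables would.

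*SAP*

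**What the plan says.** SAP 3.1.2 sets the general rule: "Baseline value will be defined as the last analysable value prior to the first IMP intake in CL2-95014-002 study". A value on the same date as that intake also qualifies. The rule gives way only to something different in SAP 3.3 to 3.5.

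SAP 3.5.2 plans three kinds of shift table:

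- By CTCAE grade, setting the "baseline laboratory evaluation relative to the worst value during the treatment period using CTCAE v5.0 grades".
- By normal range (low, normal, high), each visit against baseline.
- For the dipstick: "Shift tables for qualitative urinalysis results at each time point after the first IMP infusion will be created". No reference value is named here.

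The parent study was an induction study: SAP 1.2 describes the patients as those "who completed the CL2-95014-002 study during the induction phase". For the present study, SAP 1.2.1 says that "treatment period will start at Day 1 of the consolidation phase", and the secondary objective in SAP 1.1.2 is to "assess the safety profile of S95014 lyophilizate during the consolidation phase".

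**The concern.** The tables start in one study and end in the next. Their starting point is a value in newly diagnosed children before induction treatment (Protocol 2.2.4). Their end point is a value during consolidation. Everything that happened in induction lies between the two.

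A reader of the report will want to know which laboratory abnormalities appeared or worsened while patients received the lyophilizate in consolidation. These tables cannot answer that for a given patient, and they can mislead in either direction. Two features add to this. Safety results are presented by starting dose level in this study (SAP 2.1 and 3.5), so a shift that arose in induction is shown under a dose given only later. The parent study also used both the liquid and the lyophilized formulation (Protocol 2.2.4), so some of the change shown may have followed the liquid product.

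**Working it through.** The plan gives no figure to reproduce. The check compares the sections and then follows what a shift table can hold.

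**1. Does anything override the general baseline?** SAP 3.3 to 3.5 contain no other definition of baseline for laboratory or urinalysis data. Protocol 10.2.1.2 describes the same laboratory shift table without defining baseline. The pre-induction definition therefore applies to all three kinds of table, and to urinalysis by default.

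**2. What do the tables hold?** For one patient and one parameter, let

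- g0 = grade before the first dose in CL2-95014-002,
- g1 = grade just before the first infusion in CL2-95014-003,
- w = worst grade after that infusion.

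The planned CTCAE table gives the joint distribution of g0 and w. Worsening within consolidation is a statement about g1 and w. The by-visit low/normal/high table crosses each visit with the pre-induction value. Even if it includes inclusion and week 7 pre-dose, it gives the pre-consolidation status against the pre-induction value, and each later status against the pre-induction value. The joint distribution of pre-consolidation and later status cannot be recovered from those two. No planned table supplies it.

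**3. When do the two references disagree on direction?** Only when g0 differs from g1:

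- g0 < w ≤ g1: an upward shift is shown, with no worsening in consolidation.
- g1 < w ≤ g0: a worsening in consolidation is not shown as an upward shift.

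Hypothetical patients:

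| Parameter | g0 | g1 | w | Planned table | From start of consolidation |
|---|---|---|---|---|---|
| ALT | 0 | 2 | 2 | 0 to 2 (upward) | 2 to 2 (no change) |
| Neutrophils | 4 | 1 | 3 | 4 to 3 (not upward) | 1 to 3 (upward) |

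**4. What does not depend on the choice?** The totals by worst grade count patients by w alone. For the same patients and the same set of post-infusion values they are identical under either baseline. Only the row in which a patient is placed changes.

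**5. Is a pre-consolidation value available?** Yes. Protocol 8.2 and Table (4.1.2) 1 schedule haematology, biochemistry, coagulation and urinary tests at inclusion and before every infusion, week 7 included. The inclusion visit is the withdrawal visit of the parent study (SAP 1.2.1), so it follows induction exposure.

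**6. Scope.** Protocol Table (8.2) 1 lists:

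- haematology: 5 + 6 differential counts = 11 (absolute and percentage counted once);
- biochemistry: 23 (BUN or urea counted once);
- coagulation: 7;
- dipstick: 4.

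Blood parameters total 11 + 23 + 7 = 41. The grade-based table covers those of the 41 for which CTCAE provides grades. How many patients have g0 different from g1 is not stated and cannot be derived.

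**The case against.** The strongest reply is that this is a choice of reference and no mistake. SAP 3.1.2 names the parent study and adds a same-date rule, so it is not a drafting slip. Protocol 10.2.2.2 allows parent-study data for baseline characteristics, Protocol 17.1.3 allows them in this study's report, and Protocol 10.5 leaves analysis details to the SAP. A pre-S95014 value shows cumulative change, which a post-induction value would conceal. The objective speaks of a safety profile during consolidation and does not mention change from its start. All of this stands.

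Other outputs also cover part of the ground. Treatment-emergent events count from the inclusion visit (SAP 3.5.1), and events already reported in the parent study are not reported again unless they worsen (Protocol 8.9.1). Clinically significant laboratory abnormalities therefore reach the adverse event tables largely free of carry-over. By-visit statistics and listings of abnormal values allow partial reconstruction. This too stands, but changes that do not qualify as adverse events appear only in the laboratory outputs, and there no table pairs a patient's pre-consolidation value with later ones.

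Eligibility criteria 9 and 13 (Protocol 5.2.2) limit carry-over of major abnormalities. Lesser grades can remain, and the criteria do nothing about masking by a pre-induction abnormality that has recovered. The table templates are a separate document (SAP 1) and may add labels; they were not available here.

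A reader might go further and infer that the SAP baseline is wrong, that it contradicts the protocol, or that the consolidation safety results are unreliable. The documents support none of these. The protocol leaves baseline undefined for the shift tables, the shifts shown are correct for the reference defined, and the adverse event analysis is untouched.

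**Conclusion.** The point holds as a gap in the planned output. The existing shift tables are valid as cumulative change from before the first dose in CL2-95014-002. They cannot say for an individual patient whether a shift arose in induction or in consolidation, and the misreading can go either way. The gap covers up to 41 blood and 4 dipstick parameters; its size in patients is unknown. The study is descriptive, with no hypothesis test at risk.

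The conclusion assumes that the general baseline definition applies wherever SAP 3.5.2 gives no other, and that the table templates do not add a second reference. It does not require demoting or replacing the prespecified tables: the two references answer different questions. Label: cheap improvement.

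**What to change.** In SAP 3.5.2:

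- Add laboratory shift tables (CTCAE grade and low/normal/high) and urinalysis shift tables whose baseline is the last non-missing value before the first S95014 infusion in CL2-95014-003: week 7 pre-dose, or inclusion if that is missing.
- In the added CTCAE-grade table, take the worst value only from values after that infusion, so that the baseline value cannot also be the worst value.
- Keep the existing tables, and label them as cumulative change from before the first dose in CL2-95014-002.

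The change needs SAP wording and table shells only, with no new samples or visits. If the SAP is already final, Protocol 10.5 provides for a SAP amendment. The cost is one extra set of tables. In these, toxicity persisting from induction, and any change between inclusion and week 7 pre-dose, counts as baseline, which is why the cumulative tables should stay beside them.

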3.2. Handling of Missing, Unused, and Spurious Data

No specific imputation method will be used for missing data, unless otherwise specified.

Adverse events (AEs)

- Handling of unknown causality assessment:
 - o If a subject experience an AE with a missing causality assessment, the relationship of the AE will be counted as "related".
- Handling of unknown severity grades:

- If a subject experiences more than one AE categorized under the same preferred term, one of them is categorized as “severe” and one of them is categorized as “unknown”, the severity of this AE should be counted as “severe”.
- If a subject experiences more than one AE categorized under the same preferred term, one of them is categorized as “mild” or “moderate” and one of them is categorized as “unknown”, the severity of this AE should be counted as “unknown”. A column “UNK” should be inserted for those AEs at the end of the table (before the “Total” column if applicable).

Missing dates

If no specific management of dates is defined, missing information is substituted as shown below:

Table (3.1.2) 1 - Substitution rules of dates if no specific management is defined

Date to substitute		Substituted date
Date	./mmm/yyyy	01/mmm/yyyy
	././yyyy	01/JAN/yyyy
	././....	No substitution

Note:

./mmm/yyyy = missing day
 ././yyyy = missing day and month
 ././.... = missing date

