8.3. Definition of Adverse events

An adverse event is defined as any untoward medical occurrence in a subject participating in a clinical study, whether or not there is a causal relationship with the IMP and/or experimental procedures, occurring or detected from the date the participant signs the information and consent form, irrespective of the period of the study (periods without administration of the IMP (e.g. run-in period) are also concerned).

An adverse event can therefore be:

- any unfavourable and unintended sign (including an abnormal finding from an additional examination such as lab tests, X-rays, ECG, ...) which is deemed clinically relevant by the investigator,
- any symptom or disease,
- any worsening during the study of a symptom or a disease already present when the participant entered the study (increase in frequency and/or intensity), including the studied pathology,

and detected during a study visit or at an additional examination or occurred since the previous study visit (including relevant event reported in participant's diary or safety evaluation scale).

Of note:

Any hospitalisation for administration of anti-tumoral treatment and/or associated protocol (during or after the study) or other care measures for cancer (e.g. overnight hospital stay to receive a blood or platelets transfusion), for social reasons, educational purpose (e.g. learning of diabetes management by the participant) or routine check-up should not be considered as an adverse event and should not be reported in the e-CRF. The following procedures, whether planned before the study or not, whether leading to a hospitalisation or not, **should not be reported in the e-CRF and kept in the source data (or patient file):**

- therapeutic procedures related to a non-aggravated medical history (e.g. cataract extraction not due to an aggravation of the cataract during the study, haemodialysis sessions related to a renal insufficiency not aggravated during the study),
- prophylactic procedures (e.g. sterilisation, wisdom teeth removal),
- comfort procedures (e.g. cosmetic surgery),
- control procedures of a pre-existing condition without aggravation (e.g. colonoscopy to control the remission of colon cancer).

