8.9. Reporting procedures

8.9.1. Time frame for AE reporting

Any event meeting the above mentioned definitions (see sections 8.3 to 8.7) must be reported to the sponsor on an adverse event form if it occurred:

- before the first intake of the IMP for events related to the research
- at any time after the administration of IMP, up to the participant's withdrawal visit for all events,
- up to 30 calendar days after the participant's last intake of IMP for all ERIN, regardless of the supposed role of the research.
- irrespective of the time of onset after the end of the study in case of serious adverse event related to the research.

[figure not shown]
Of note, events occurring between the signature of the informed consent and the first administration of the test drug for which the investigator does not consider an association with

¹ Instrumental Activities of Daily Living (ADL) refer to preparing meals, shopping for groceries or clothes, using the telephone, managing money, etc.

² Self-care ADL refer to bathing, dressing and undressing, feeding self, using the toilet, taking medications, and not bedridden”.

any procedure/condition required by the study protocol must be reported as **medical history** or as signs and symptoms related to the studied disease in the dedicated form of the CRF.

For a given patient, medical histories and adverse events already reported in the initial CL2-95014-002 study will not be reported in the eCRF, except in case of worsening.

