3.5.1. Adverse Events

A treatment-emergent adverse event (TEAE) is defined as any untoward medical occurrence in a subject who received IMP (S95014), which occurs within the period from the Inclusion visit, until 30 days after the last S95014 infusion, or the date of withdrawal, whichever is earlier. TEAE will be assessed according to the National Cancer Institute (NCI) Common Terminology Criteria Adverse Events (CTCAE) v5.0. Clinically significant laboratory abnormalities will be classified into Common Terminology Criteria (CTC) grade according to CTCAE v5.0 and will be reported as adverse events if they are associated with signs and symptoms or, clinically significant in the investigator's opinion except if related to the disease, if they require curative therapies, if they induce change of study treatment administration. All analyses described below will be based on TEAEs, if not otherwise specified.

Adverse events will be summarized in hierarchical tables, presenting the number and percentage of subjects having at least one AE, and having at least one AE in each primary system organ class and for each preferred term using MedDRA coding. AEs will be sorted by descending frequency, and alphabetically where frequency is tied. Such summaries will be produced for all AEs, serious adverse events (SAEs), grades 3 or 4 AEs, AEs leading to study treatment discontinuation, and AEs leading to dose-adjustment or interruption of any of the drugs of the treatment. All of these summaries will be by system organ class, preferred term, starting dose level if applicable and, in some case, worst grade. Most of the summaries will be produced twice, once for all events regardless of study treatment relationship, and once for events suspected to be study treatment related. All deaths will be listed and summarized. All AEs will be listed, and any other information collected (e.g., start/end dates and duration of adverse event, severity or relatedness to study medication) will be listed as appropriate.

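### SAP 3.2 has no date rule for adverse events: if its default is used to derive TEAE status, a day-missing onset in the inclusion month drops out of the TEAE tables

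*SAP*

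**What the plan says.** SAP 3.2 introduces its date table as a fallback: "If no specific management of dates is defined, missing information is substituted as shown below". Under the table a missing day becomes the 1st of the recorded month, a missing day and month become 1 January of the recorded year, and a fully missing date is left as it is. The AE rules in the same section, like those in Protocol 10.3, deal only with missing causality and unknown severity.

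SAP 3.5.1 defines a TEAE by calendar limits: "from the Inclusion visit, until 30 days after the last S95014 infusion, or the date of withdrawal, whichever is earlier". It then says "All analyses described below will be based on TEAEs", unless otherwise specified. It does not say how a partial onset date is to be compared with those limits.

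Protocol 8.9.1 settles which events can be in the database. Before the first infusion, only events related to the research are reported as AEs. After it, collection runs "at any time after the administration of IMP, up to the participant's withdrawal visit for all events". Beyond the withdrawal visit two narrower streams remain. Events requiring immediate notification are reported "up to 30 calendar days after the participant's last intake of IMP for all ERIN", and related serious events "irrespective of the time of onset after the end of the study in case of serious adverse event related to the research". The same section says that "medical histories and adverse events already reported in the initial CL2-95014-002 study will not be reported in the eCRF", except on worsening.

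**The concern.** The Inclusion visit is the withdrawal visit of CL2-95014-002 (SAP 1.2.1), so it can fall on any day of the month. Moving a day-missing onset to the 1st of its month therefore puts it before inclusion for every patient not included on the 1st, provided the onset is in the inclusion month. The event then fails the TEAE test although it began during this study.

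Two features of the plan make that outcome hard to defend. First, AEs already recorded in the parent study are not entered again unless they worsen, so a partly dated AE in this eCRF is most likely new. Second, SAP 3.2 counts an AE with missing causality as related, so a gap in the data does not remove a safety signal there. The date default does the opposite at the opening of the window.

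Assessing safety is the only objective with planned analyses. A lost record changes a patient count only when it was that patient's only event in the table row.

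**Working it through.** The documents give no number or rate of partial AE dates, so there is no plan figure to reproduce. The rule can be tested on the calendar.

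**Worked example.** Inclusion is on 10 March and true onset on 20 March, recorded without the day. The substituted onset is 1 March, which is before 10 March, so the event is not a TEAE.

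**Inputs from the documents.** Infusions run from week 7 to week 27, so first to last is 20 × 7 = 140 days. The window closes at the earlier of 30 days after the last infusion and the date of withdrawal. The withdrawal visit may be up to 30 days after the last dose.

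**Assumptions not in the documents.** The gap g from inclusion to first infusion is 0, 7, 14 or 21 days. The window closes 30 days after the last infusion, or at 14 days with an early withdrawal visit. Inclusion is equally likely on each of the 365 days of 2021. Onsets spread evenly over days. They are counted from the first infusion, because before it only research-related events are AEs.

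**Opening edge.** In a month of m days, with inclusion on day d ≥ 2, the lost onset days run from d + g to the month end. Summed over d this is k(k − 1)/2 with k = m − g. A 365-day year has seven months of 31 days, four of 30 and one of 28. For g = 0 the total is 7 × 465 + 4 × 435 + 378 = 5,373. Onset days at risk are 365 × (140 + 30 + 1) = 62,415, or 365 × (140 + 14 + 1) = 56,575.

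| Gap (days) | Lost days | Lost, window to day 30 | Lost, window to day 14 |
|---|---|---|---|
| 0 | 5,373 | 8.61% | 9.50% |
| 7 | 3,154 | 5.05% | 5.57% |
| 14 | 1,523 | 2.44% | 2.69% |
| 21 | 480 | 0.77% | 0.85% |

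These are shares of day-missing onsets only. Within the inclusion month itself, counted from the Inclusion visit, 93.6% of onset days are lost; the rest belong to inclusions on the 1st.

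**Per 1,000 AEs.** If 1 to 5% of in-window onsets lacked the day (a further assumption), the loss runs from 1% × 0.77% = 0.08 per 1,000 to 5% × 9.50% = 4.8 per 1,000. With a 14-day gap and 1% partial dates it is 0.24 to 0.27 per 1,000.

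**Year-only dates.** An onset in the inclusion year goes to 1 January and is lost unless inclusion was that day. Counting onset days from the Inclusion visit, for gaps of 0 to 14 days and a window closing at day 15 or day 30, 74.5 to 78.5% of in-window days are lost. Such dates should be rare, since infusion visits are mostly two weeks apart.

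**Fully missing onsets.** No date is substituted, and no rule says whether the event is a TEAE.

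**Closing edge.** An onset after the window but in the month in which it closes is moved in. Over the 30 days after closure this is 5,373/(365 × 30) = 49.1% of day-missing onsets. If the window closes at day 14, it is 4,208/(365 × 16) = 72.1% over the 16 days to day 30. If the window closes at day 30, routine collection of immediately notified events stops the same day, so the 49.1% applies only to late research-related serious events.

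**Test of the remedy.** Setting the onset to the later of the 1st of the month and the inclusion date loses no in-window onset in any of the eight scenarios. It leaves the closing edge at 49.1%, so that edge needs its own step.

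**The case against.** The table in SAP 3.2 is only a fallback, and SAP 3.5.1 defines a TEAE by when the event occurs. Nothing says outright that the TEAE flag uses a substituted date, and the separate TLG document may hold a specific rule. This stands as a condition on the point. It does not remove it, because the SAP refers to no other rule for AE dates, and a programmer following it would apply the default.

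The size rests on assumptions. The upper figure of 4.8 per 1,000 combines the highest assumed partial-date rate, no gap and a day-14 withdrawal. Frequent visits and data queries (Protocol 14.2) should keep missing days uncommon. This also stands.

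The closing-edge percentages could mislead. The records at risk are mainly events that must be notified within 24 hours, entered at once and supported by documents (Protocol 8.7, 8.9.2.1, 8.9.2.5). These are the least likely to lack an onset day, and counting one too many is conservative. A reader might infer that the two edges matter equally; the documents do not support that.

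A reader might also infer that lost events vanish altogether, or that they certainly survive in the AE listing and the summary of deaths. Neither can be asserted. The sentences on listings and deaths follow the TEAE restriction in SAP 3.5.1, and whether they escape it is a matter of reading.

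**Conclusion.** The point holds, conditionally and at low weight. Where TEAE status is derived from the substituted date, the default wrongly removes day-missing onsets in the inclusion month and year-only onsets in the inclusion year. That is anti-conservative and at odds with the SAP's own handling of missing causality. About 0.8 to 9.5% of day-missing in-window onsets would be lost, given evenly spread onsets and a gap of 0 to 21 days. The number of partial dates is unknown and the overall effect is probably small. The opposite error at the closing edge is minor.

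A reader might conclude that the TEAE tables will understate AE rates overall. The documents do not support that: the two edges err in opposite directions, neither frequency is known, and the study is single-arm and descriptive. What is established is a gap that is easy to close before database lock.

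**What to change.** Add an AE-specific rule to SAP 3.2:

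- A partly or fully missing onset counts as treatment-emergent unless its known date parts, or its end date as recorded and not as substituted, show that it began before the Inclusion visit or after the end of the TEAE window.
- Where a substituted onset is needed, use the later of the earliest possible date and the inclusion date. List the date as collected.
- Where the recorded month spans the end of the window, query it. Protocol 8.3 ties an AE to being "detected during a study visit or at an additional examination or occurred since the previous study visit", so the visit or contact at which it was first reported can help. If it stays unresolved, count it as treatment-emergent with a footnote.

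If the TLG document already holds such a rule, a cross-reference in SAP 3.2 is enough.

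The cost is a few lines of text, one derivation and an occasional query. The downside is that a few events that truly began outside the window may be counted.
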